### 2. SYNOPSIS

TITLE	Effect of Swallowing Therapy on Efficiency of Eating and Drinking in People with Parkinson’s Disease using Principles of Motor Learning and Ultrasound Biofeedback
CLINICAL PHASE	I/II
STUDY TYPE:	Behavioural intervention
PRIMARY HYPOTHESES	Participants will show an improvement in swallowing outcomes with the use of rehabilitation combining principles of motor learning and ultrasound biofeedback. No improvement in control outcomes will be observed.
DESIGN	Part 1 - Single Case Experimental Design to determine feasibility of treatment paradigm in a single participant with PD followed by Part 2 - a multiple baseline within participants Single Case Experimental design to determine treatment efficacy.
BLINDING/MASKING	This is a pilot, behavioural intervention trial. Therefore, treating clinicians and participants cannot be blinded to intervention.

	Clinicians assessing outcome measures will be blinded to the sequence in which the probe data is collected and the stage of the study the participant is in.

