### **4.2 Hypotheses:**

People with Parkinson's Disease with dysphagia who participate in a four-week intervention using ultrasound visual feedback and principles of motor learning will show improvements in their swallowing efficiency (i.e., reduction in time taken to swallow liquid and food)

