### **6.14 Statistical analyses**

As per standard procedure for single case within participant studies, experimental and control measures will first be graphed and visually inspected for change. If the visual inspection indicates change over time, statistical analysis will be completed. As multiple, repeated measures will be taken for each participant, the data will first be analysed for correlations. If the correlation coefficient was not significant, the assumption of independence in measurements will be made, and effect sizes within participant will be calculated using  $d_2$  as this measure is appropriate for single case data (Beeson & Robey, 2006).

In the presence of serial dependency between data points, the data will be analysed using percent of nonoverlapping data (PND) (Scruggs, Mastropieri & Casto, 1987). PND is a commonly used calculation to measure change in measures taken across research phases. The highest data point in the baseline (A1) phase is compared across all research phases. The number of data points either above or below that value is calculated as a percentage of the total number of data points. The higher the number of nonoverlapping data points, the stronger the effect.

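### Section 6.14 anchors PND on the highest baseline value for every measure, which is the worst value for outcomes scored as times: an unchanged participant who reached this analysis would average about 75–88%

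*Protocol*

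**What the plan says.** Section 6.14 sets out a sequence. Graphs come first: "If the visual inspection indicates change over time, statistical analysis will be completed". If the repeated measures are not significantly correlated, the effect size is d2. Otherwise PND is used: "In the presence of serial dependency between data points, the data will be analysed using percent of nonoverlapping data".

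PND is then defined in three steps:
- Anchor: "The highest data point in the baseline (A1) phase is compared across all research phases".
- Count: "The number of data points either above or below that value is calculated as a percentage of the total number of data points".
- Interpretation: "The higher the number of nonoverlapping data points, the stronger the effect".

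No other anchor is given for any measure, and no side (above or below) is assigned to any measure.

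Section 4.2 gives the direction for swallowing efficiency: "reduction in time taken to swallow liquid and food". Section 6.5 names the Timed Water Swallow Test (TWST) and the Test of Masticating and Swallowing Solids (TOMASS) as primary outcomes without a scoring metric. Its secondary measures include times for solid boluses, swallow counts and meal time. The Synopsis adds the contrast with the speech measures: "No improvement in control outcomes will be observed".

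**The concern.** A nonoverlap statistic asks how many later points beat the best baseline point. Where a shorter time is better, the best baseline point is the lowest. Section 6.14 uses the highest, which is the easiest point to beat.

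The words allowing points on either side change the side counted but not the anchor. Counting below the highest A1 value takes in most values that look just like baseline. Counting above it makes slower swallowing count as effect. Neither is a usable measure of improvement for an outcome scored as a time or a swallow count.

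At stake is the effect size for the swallowing outcomes whenever the analysis takes the PND branch. A high percentage could be reported with no change, or with worsening, which section 7.2.1 itself names as a possibility because the disease progresses.

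**Working it through.** The protocol states no PND value or cut-off, so there is no figure to reproduce. The check asks what the written rule returns when nothing changes.

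**Inputs from the protocol** (Probes, section 6.2): m = 6 or 9 A1 probes; Phase B has 2 probes a week × 4 weeks = 8.

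**Assumptions:** the outcome is scored as a time; the denominator is the 8 Phase B points; probes are equally spaced and normally distributed. The protocol gives no serial correlation, so a stationary AR(1) series with lag-1 correlation 0.3 to 0.8 is used as a range.

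**Independent-data limit.** For a later point from the same continuous distribution as the m baseline points:
- P(below the highest of m) = m/(m+1): 6/7 = 85.7%, 9/10 = 90.0%.
- P(below the lowest of m) = 1/(m+1): 1/7 = 14.3%, 1/10 = 10.0%.

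**With serial dependency**, by simulation (200,000 series per setting), mean percentage of Phase B points:

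| Lag-1 correlation | A1 probes | No change, below highest A1 (as written) | No change, below lowest A1 (correct anchor) | Times 1 SD longer, below highest A1 |
|---|---|---|---|---|
| 0 | 6 | 86 | 14 | 59 |
| 0.3 | 6 | 83 | 17 | 55 |
| 0.5 | 6 | 81 | 19 | 52 |
| 0.8 | 6 | 75 | 25 | 40 |
| 0 | 9 | 90 | 10 | 66 |
| 0.3 | 9 | 88 | 12 | 63 |
| 0.5 | 9 | 86 | 14 | 60 |
| 0.8 | 9 | 81 | 19 | 48 |

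Over correlations 0.3–0.8 an unchanged participant therefore averages 75–88% as written, against 12–25% with the correct anchor.

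**The other reading.** If points above the highest A1 value are counted, times that shorten by 2 SD score 0.2–0.7%. The correct anchor gives that same improvement about 70–87%.

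**Only series that pass a dependency test.** The protocol names no test. Taking |r₁| > 1.96/√T over the T = 14 or 17 A1 and B points (thresholds 0.52 and 0.48), unchanged series that pass average about 68–83% as written and 17–32% with the correct anchor. They are 5–8% of series at correlation 0.3 and 47–65% at 0.8.

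**Denominator.** Section 6.14 refers to all research phases and the total number of points. If the A1 points are included, the A1 phase counts towards its own nonoverlap: for independent data (5 + 8 × 6/7)/14 = 85% and (8 + 8 × 9/10)/17 = 89% as written. With the correct anchor no A1 point can count, so the ceiling would be 8/14 = 57% or 8/17 = 47% even for a perfect response. The denominator wording therefore needs repair as well.

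**The case against.** Several points on the other side have weight.

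- **Two gates come before PND.** A visibly flat series may never reach a statistic, and a series without significant correlation goes to d2. This stands. A reader might take 86–90% against 10–14% as the size of the problem, but those are the independent-data values, and section 6.14 sends such data to d2. Nor do the documents support saying that unchanged participants would generally be reported as improved. Still, the visual gate asks for change and not for improvement, so a drifting or worsening series can pass it, and neither gate makes the index behind it valid.
- **The hypothesised pattern is not built in.** A reader might infer that the rule must produce high swallowing PND with low control PND. That happens only if the analyst counts below for swallowing and above for controls where higher is better. The protocol does not state that choice, and using one side throughout gives no such contrast under no change.
- **Control directions are not stated.** It is tempting to say the highest A1 value is right for all the speech controls. That is reasonable for maximum phonation time, but the protocol does not establish it for others, such as speech rate.
- **The primary outcomes might be scored as rates.** Section 6.5 gives no metric for TWST or TOMASS, and one secondary sip measure is in ml/s, where the highest value is the best. Section 4.2 supports reading them as times but does not exclude a rate.
- **This is a small pilot and PND is a descriptive fallback** with no decision threshold. True, and it limits the consequences, but the percentage is still to be read as strength of effect.

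The authors may intend the usual direction-specific PND. The text does not say so: it fixes an anchor, and that anchor is wrong for time outcomes.

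**Conclusion.** The point holds as an error in the written rule, not as detail left to a later plan. For any outcome scored as a time or a swallow count, section 6.14 uses the worst baseline value as reference, contrary to the direction in section 4.2, and neither side of the count repairs it.

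Within the branch where PND applies, an unchanged participant would average about 75–88% instead of 12–25%, or about 68–83% instead of 17–32% among unchanged series passing the assumed dependency test. A 1-SD worsening would still score about 40–63%. On the opposite reading, a 2-SD improvement would score under 1%. These figures rest on the assumed AR(1) correlation, the Phase B denominator and time scoring, and they do not model the visual-inspection gate.

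If the analyst counts below for swallowing and above for controls where higher is better, the artefact would mimic the hypothesised contrast between swallowing and control measures. That is conditional on a choice the protocol leaves open.

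**What to change.** Amend section 6.14 and add a direction column to the outcome list in section 6.5:

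1. State the scoring metric and direction of improvement for each measure before any data are graphed.
2. Where lower is better (TWST and TOMASS if scored as times, bolus times, swallow counts, meal time), take the lowest A1 value as reference and count only points below it.
3. Where higher is better (for example maximum phonation time, or any swallowing measure scored as a rate such as ml/s), take the highest A1 value and count only points above it.
4. Compute the percentage over the points of the phase being compared, not over all data points.

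The cost is a few sentences and one column, with no new data. The downside is that reported PND values for time outcomes will be lower than under the present wording.

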## **7. ETHICAL CONSIDERATIONS (SEE DATA, SECTION 10 FOR PRIVACY AND CONFIDENTIALITY)**

### **7.1 Conformance with the principles of the “Declaration of Helsinki”, Good Clinical Practice (GCP) and within the laws and regulations of the country in which the research is conducted**

The University of Sydney HREC is the primary ethics committee for this clinical trial. The ethical committee will provide ethical oversight and will ensure the current clinical trial is evaluating the research in respect to the NHMRC National Statement. Complying with the National Statement ensures we are complying with the Declaration of Helsinki. All CIs have undertaken Good Clinical Practice (GCP) Training. The clinical trial will also comply with the National Health and Medical Research Council (NHMRC) regulations.

### **7.2 Potential Risks and Proposed Benefits**

#### *7.2.1 Potential Risks*

It is unlikely that participants will experience any harm when receiving therapy. Ultrasound as a biofeedback in a skill-based training targeting orolingual control has also been safely used in the head and neck cancer and other populations.

This is a relatively low-risk project and does not pose significant foreseeable risks to the participants. It may involve mild distress sometimes as tasks may be difficult for the participant. However, speech pathology care in this study is not different from usual practice.

The participants may experience fatigue and frustration during assessments or treatment. The speech pathologist will note signs of fatigue or frustration and give the person a short break if these occur.

As this is a trial study with adults who have a neurodegenerative disease, there is a risk of no improvement or decline in swallow function at the end of the study due to the progression of the disease. The participants are informed of this at recruitment. Breaches of privacy or confidentiality may pose a risk. This is covered in Section 10 Data Management.

#### *7.2.2 Proposed Benefits*

The participants will receive therapy and attending therapy may have a therapeutic effect. They will receive a free summary report of their swallowing therapy and recommendations

#### *7.2.3 Responsibility for liability of injury*

The university will be the sponsor of the study and will retain the liabilities associated with the conduct of the study.

### **7.3 Recruitment**

#### *7.3.1 Recruitment Method*

The recruitment method was detailed in Section 6, Page 9.

#### *7.3.2 Dual or unequal relationships, potential for coercion or inducement*

The participants will not be approached directly by any of the research team members to protect them against potential coercion. Participants will also be informed that if they decline to participate or withdraw from the study, this will not affect their relationship with the research team or the University of Sydney.

### **7.4 Informed Consent**

Participants will be informed about the study and given the Patient Information Statement (PIS) and Participant Consent Form (PCF). The PIS details what the study is about, the researchers involved, the role of the participant, benefits and risks of their involvement and details regarding participant withdrawal.

The participants will be told their participation is voluntary. They are free to decline to attend the study and withdraw from it at any time. The participant can choose whether they want to sign the consent form. If the participant declines to participate in the study, they are assured that this will not impact their relationship with the research team members, The University of Sydney and its staff.

The participant will be provided with the name and contact details of the chief investigator if they require further information. They will also be provided with the contact details of the University of Sydney Ethics committee if they have any concerns or complaints about the study.

### **7.5 Clinical governance**

The clinical governance for the project is provided by the Faculty of Medicine and Health Clinical Governance committee. The protocol will be added to the existing SPEECH Clinic Model of Care.

## **8. SAFETY CONSIDERATIONS**

### **8.1 Adverse event definition, risk assessment and mitigations**

An adverse incident is a harmful, unpleasant, or undesirable response, reaction, or outcome experienced by a research participant or researcher. In the context of this study, Serious Adverse Events include choking or chest infection resulting in hospitalisation or death.

The risk of serious adverse events is no greater than if the participant does not take part in this study. Participants in this study will be medically stable and eating and drinking in the community. Additionally, there is an exclusion criteria excluding participants who have a recent serious upper respiratory tract infection, and the therapy protocol will be carried out by a qualified and experienced speech pathologist with current CPR certification.

The researcher will contact the participants one day prior to each treatment session to ask about their health and discuss postponing the session and referral to their GP if they are unwell. The researcher will also ask the participant about their health again at the beginning of each session to confirm that they are fit to continue. If there are any concerns, they will discuss postponing the session and referral to their GP or other health practitioner with the participant.

Other potential anticipated adverse events include fatigue from the intensity of the therapy protocol and feeling full or nauseous from having to eat or drink as part of the therapy. These risks will be mitigated through:

- scheduling sessions at least 2 hours after a meal and taking their medication as normal
- reminding participants to continue with their current medication regime and that it should not be impacted by this study participation
- informing participants beforehand that they will need to eat and drink during the therapy sessions.
- and regular breaks in the session

### **8.2 Assessment and Documentation of Adverse Events**

Participants will be advised that they should report any adverse events including fatigue, pain, nausea, vomiting, fever, cough, cold, throat irritation.

In the event of a medical emergency (i.e., a serious adverse event related or unrelated to the study), an ambulance will be called, security staff at SWHB will be notified and SWHB safety procedures followed.

In either case, the adverse event or serious adverse event will be reported in Riskware (and technology relevant to the site), to the HREC and ANZCTR

### **8.3 Adverse event reporting including any special requirements for serious or significant adverse events**

All adverse events will be immediately reported to the Chief Investigator and recorded. The University of Sydney procedures for reporting serious adverse incidents will be followed. Standard procedures for completing and submitting HREC adverse event templates and contacting the HREC office directly will be completed within 72 hours. For serious adverse events, this timeline will be within 24 hours.

## 9. CONSUMER REFERENCE GROUP

Participants within the study will serve as a consumer reference group within the pilot by providing feedback on the intervention based on the theoretical framework of acceptability (TFA). Their involvement as a consumer reference group is included in the participant information statement.

## 10. DATA MANAGEMENT

### 10.1 Data collection and storage

Research data, including ultrasound recordings, video recordings of the assessment and treatment sessions, and outcome measures or session data will be collected and stored electronically. Identification codes will replace names in all files. Names, addresses, phone and email details and dates of birth will be stored on a separate password protected file only available to the chief investigator and the PhD student.

Participant information, intervention conditions and outcome measures will be collected and stored on REDCap during the project. Video and audio recordings from the assessment, probes, and treatment sessions will be encrypted and stored on the University's enterprise edition of OneDrive immediately by the PhD student during the project and deleted from the recording device immediately. All other research and study materials (e.g., ethics approval, study advertisements, information sheet) will also be stored on the University's enterprise edition of OneDrive during the project.

On OneDrive, there will be a README.pdf file in each folder which will provide the context of the files within the folder, the naming system of the files, the version controls as well as author attribution and time/date stamps.

Post-completion of the project, all research data will be transferred to and stored in the University's Research Data Store (RDS). Data on OneDrive and REDCap will be deleted.

The data collection procedures will be monitored to ensure the accuracy of the data. Data collection monitoring includes monitoring of the consistency of data analysis, quality of video recordings, and the timeframes for uploading videos to the data storage after each therapy or assessment session. Data collection procedures are discussed at supervision meetings and adjustments are implemented where required.

### 10.2 Data retention and archiving process

Deidentified study data (e.g., demographic information, outcome measures) will be archived on Open Science Framework. Identifiable study data (e.g., videos of faces and voices) will be kept for 15 years after the research study is completed in the RDS, as the study is a clinical trial. This is in adherence to the university's research code of conduct and the faculty's research data management provisions. At the end of this time the project materials will be permanently deleted from the RDS.

### 10.3 Participant Confidentiality

Access to REDCap, OneDrive and RDS will be through the unikey and limited to unikey holding HREC approved project team members. User rights on REDCap will be managed

under the user rights settings for the project. Fields containing identifying data will be highlighted and located on an instrument that can be viewed only by designated members (CI, PhD student). Patient data will only reviewed in a secure setting (e.g., private room) over secured internet connection (through university VPN) and headphones will be used to review any audio or video files from the therapy sessions, probes or assessment.

#### **10.4 Data Security Steps**

Access to REDCap, OneDrive and RDS will be through the unikey and limited to unikey holding HREC approved project team members. User rights on REDCap will be managed under the user rights settings for the project. Fields containing identifying data will be highlighted and located on an instrument that can be viewed only by designated members.

#### **10.5 Future Use of Data**

Adhering to principles of open science, data from this study will be deidentified and shared on Open Science Framework which collects and provides global access to self-archived research. During the informed consent process, participants will be notified of the above and asked if they consent to:

- their deidentified data (e.g., a datasheet containing demographic information, outcome measures) being considered for use in future research projects. Video and audio files will not be uploaded.
- being informed about other research projects.
- sharing their deidentified data on Open Science Framework to allow researchers to use this data in the future for other studies or additional analysis

#### **10.6 Data storage at the conclusion of the clinical trial**

At the conclusion of the study, all data will be transferred and stored on the RDS and deleted from all other storage. After 15 years, identifiable data of all patients and all data of patients who did not consent to their data being shared on the Open Science Framework will be securely deleted.

#### **10.7 Quality Management**

The PhD student will be responsible for ensuring the quality of processes, data, and documentation associated with the study. Data will be checked for quality and completeness as it is uploaded on university-managed storage infrastructure.

### **11. FINANCIAL**

This study is not externally funded and will be completed as part of a PhD. Equipment required for the study are readily available at the University of Sydney.

### **12. PUBLICATION POLICY / DISSEMINATION OF RESULTS**

This work will be reported in one or more journal articles and conference papers. Authorship will follow the Contributor Roles Taxonomy (Credit) and will be determined by the nature and extent of their contributions to the papers.

The findings from the study will also be disseminated to clinicians, researchers, and policy makers through the following platforms: (a) national and international conferences, (b) workplace seminars and (c) special interest groups associated with dysphagia, rehabilitation, or Parkinson's Disease. Participants will receive an email at the end of the study with a lay summary of the results of the study.

